Originally described more than 40 years ago, MSCs reside in almost all connective tissues [18]. More recently, there has been an increasing awareness that MSCs have a number of interesting secretory paracrine bystander characteristics including anti-inflammatory, anti-apoptotic, immunomodulatory, angiogenic and trophic (tissue-regenerating) properties. Notably, MSCs have shown promising results in preclinical studies for the treatment of xerostomia, including radiation-induced xerostomia [19].

The objectives of the current trial are to assess the safety and feasibility of autologous adipose tissue-derived MSCs administered for radiation-induced salivary gland hypofunction and

xerostomia in head and neck cancer patients. Head and neck cancer is the sixth most common malignancy worldwide, and the majority of these patients are due to advanced disease stage at presentation treated with chemo-, radiotherapy, or both [20,21]. The project can potentially help to develop a clinically relevant treatment option for the growing number of patients suffering from xerostomia after radiotherapy.

Methods and materials

Primary outcome

Primary outcome is safety, including adverse events (AEs) and severe adverse events (SAEs). All measures of AEs will be graded according to Common Terminology Criteria for Adverse Events (CTCAE) [22]. Since this is a local treatment with ASCs the primary safety measures are:

- Pain at injection site (Grade 1: Mild pain, grade 2: Moderate pain; limiting instrumental activities of daily living (ADL), grade 3: Severe pain; limiting self-care ADL)
- Oral discomfort (Grade 1: Mild discomfort; not interfering with oral intake, grade 2: Moderate pain; interfering with oral intake, 3: Disabling pain; tube feeding or total parental nutrition indicated)
- Infection (Grade 1: Localized; local intervention indicated, grade 2: Oral intervention indicated (antibiotic, antifungal, antiviral), grade 3: IV antibiotic, antifungal or antiviral indicated; or radiologic, endoscopic or operative intervention indicated, grade 4: life threatening consequences; urgent intervention needed)

Secondary outcomes

- Unstimulated and stimulated whole saliva and selective submandibular saliva flow rate and composition of saliva.
- Complaints of xerostomia as evaluated by a physician and patient questionnaire.
- Measurement of volume, fibrosis, and vascularisation change of submandibular glands based on magnetic resonance imaging (MRI).

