At baseline, one and four months after treatment, unstimulated whole saliva will be collected using the spitting method [29] where participants spit their saliva into a collection container over a period of 15 minutes. The salivary flow rate (SFR) (ml/min) is determined as the increase in weight of the container divided by the collection time in minutes. After the collection of unstimulated saliva, the subjects are instructed to chew on 1 g of sterile paraffin wax. Participants will chew for 60 s, and clear the oral cavity for saliva. Subsequently, as the glands are now in a stimulated state, participants will continue chewing the paraffin wax and expectorate into a saliva collector for the duration of five minutes. Subsequently, testing of the submandibular glands will be performed. To assess ASC efficacy on the submandibular glands, saliva is also collected directly from the floor of the mouth in an unstimulated and stimulated state. The flow rate of the submandibular glands will be assessed by the swab method with cotton rolls placed buccally in each maxillary molar region to block the orifices of the parotid ducts and cotton rolls under the tongue in the floor of the mouth to collect submandibular/sublingual saliva. Immediately prior to the start of collection participants will be asked to swallow. Unstimulated saliva testing will be performed with neutral

cotton rolls(Salivette ®, Sarstedt, Nümbrecht, Germany) and stimulated saliva testing with cotton rolls with 20 mg citric acid (Salivette with citric acid ®, Sarstedt, Nümbrecht, Germany). For both measurements, collections takes place during a period of 3 min. Saliva flow rates are determined by weight (1 g equals 1 ml of saliva) with cotton rolls weighed before collection and reweighed after. The flow rates are calculated as the increase in weight during collection and expressed as millilitres per minute. Saliva from the cotton rolls will be extracted by centrifugation (1500 g) and analyzed for its composition. From each of these collections, saliva will be aliquoted and stored at -80°C.

Chemical analysis of saliva

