Whole saliva contains a large number of bacteria and epithelial cells, as well as gingival crevicular fluid. Therefore, whole saliva is normally not suited for the analysis of sensitive chemical parameters. For this purpose, non-contaminated selectively collected saliva from individual glands: i.e. parotid and submandibular/sublingual saliva is more suitable. The following analyzes will be performed on the collected saliva: pH and bicarbonate by ionic balance estimation [30], sodium, potassium, calcium, phosphate, chloride and fluoride [16], total protein, selected proteins [31] and amylase [32]. Chemical analysis will provide an estimate of dental and mucosal protective capacity of the saliva before and after treatment.

MRI analysis of the submandibular glands

A 3.0-Tesla 4-channel head coil and a dual-channel neck coil are employed to obtain hsMRI images of subjects (Siemens Magnetom Verio; Erlangen, Germany).

Volumetric and tissue-specific analysis will be performed based on axial and coronal sequences with 72 slices and 4-mm slice thickness including diffusion weighted and dynamic contrast-induced sequences. The contrast agent used is Gadolinium (“Gadovist”).

Statistical analyses

Data will be analyzed with SPSS v. 24 (IBM) or R statistics. We will use Excel or Access databases for collecting and entering data. All data will be double-entered. End of trial is defined as: last patient’s last visit (LPLV).

The results on salivary flow rate will be calculated as a percentage change in salivary flow rate (from baseline) in the group of participants given ASCs compared to the change-score in the control group.

Histologically, the composition of glandular tissue in the submandibular gland will be calculated

from before (baseline) and four months after the intervention (Figure 1). The differences between the intervention and the placebo group will be calculated by a non-paired t-test, alternatively a non-parametric test, if the conditions for parametric tests are not present. Differences are considered statistically significant if the two-sided p-value is less than 0.05.

Sample size calculation

The following sample size determination is based on a non-paired t-test. The minimal change in salivary flow rate that we want to be able to determine is 50%.

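### pH and bicarbonate are to be read on saliva spun from citric-acid rolls, so in that one collection pH largely reflects the stimulus and shifts with flow alone

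*Combined protocol and SAP*

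**What the plan says.** The combined protocol and SAP, under Assessment of salivary flow rate and objective treatment outcome, describes two roll collections from the floor of the mouth. The unstimulated one uses neutral rolls. The other is "stimulated saliva testing with cotton rolls with 20 mg citric acid". The timing sentence covers the two together: "For both measurements, collections takes place during a period of 3 min". Next comes "Saliva from the cotton rolls will be extracted by centrifugation (1500 g) and analyzed for its composition", with no exception for the acid-loaded rolls, and then "From each of these collections, saliva will be aliquoted and stored at -80°C".

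Chemical analysis of saliva prefers selectively collected gland saliva to whole saliva for sensitive parameters. It then states: "The following analyzes will be performed on the collected saliva: pH and bicarbonate by ionic balance estimation", followed by electrolytes, proteins and amylase. Citrate is not on the list, and the calcium assay (total or ionised) is not specified. The stated purpose is: "Chemical analysis will provide an estimate of dental and mucosal protective capacity of the saliva before and after treatment".

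Composition is a named secondary outcome: "Unstimulated and stimulated whole saliva and selective submandibular saliva flow rate and composition of saliva". No correction of composition for flow, collected volume or residual acid is described.

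**The concern.** Acid left in a roll comes out with the saliva when the roll is spun. In the citric-acid collection, the measured pH then describes a mixture of stimulus and secretion. Two things follow.

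- **Loss of information.** If the acid greatly exceeds the buffer that the gland supplies, real differences between patients or visits are compressed, and little native bicarbonate remains to be measured.
- **A path from flow to pH.** The mass of acid is fixed, so its concentration falls as collected volume rises. If ASC raises flow, pH in that arm rises even when the gland secretes the same fluid. Randomisation does not remove this, because the artefact runs through the treatment's own effect on flow. The plan reads the chemistry as protective capacity, so a flow effect could be counted a second time as better saliva quality.

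**Working it through.** The plan gives no expected pH, bicarbonate or residual acid, so there is no figure of its own to reproduce on this point. Its sample size does reproduce: 58/√2 = 41, and 2 × (1.96 + 1.28)² × 41²/50² ≈ 14.1, hence 15 per arm. It does not depend on the chemistry.

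**Inputs from the documents**
- 20 mg citric acid and 3 minutes of collection (Assessment of salivary flow rate).
- 0.05-0.20 ml/min (Eligibility criteria). This is unstimulated whole saliva, the only flow range given, and is used here as an anchor.
- A 50% change in flow (Sample size calculation).

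**Assumptions not in the documents**
- One 20 mg charge per collection; more loaded rolls would mean more acid.
- Molar mass 192.12 g/mol; citric acid pKa 3.13, 4.76 and 6.40; carbonic acid pKa 6.1 in a closed system.
- Native bicarbonate 5-30 mM.
- 10-100% of the acid recovered in the spun fluid.
- Stimulated submandibular flow of 0.05-0.20 ml/min, extended to 1.0 ml/min to test sensitivity.

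**Step 1: amount of acid.** 20/192.12 = 0.104 mmol, or 3 × 0.104 = 0.312 mEq.

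**Step 2: concentration.** C = recovery × 0.104 mmol / (flow × 3 min). At 0.10 ml/min the volume is 0.30 ml, so C = 0.104/0.30 = 347 mM with full recovery and 35 mM with 10%. Across 0.05-0.20 ml/min with full recovery, the acid amounts to between 17 and 416 equivalents per equivalent of native bicarbonate.

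**Step 3: pH.** Solve the charge balance [H⁺] + B = [OH⁻] + [HCO₃⁻] + C·z, where B is native bicarbonate and z is the mean citrate charge at that pH. Then replace C by C/1.5 for a 50% rise in flow, which cuts the acid concentration by one third.

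| Acid recovered | Flow, ml/min | Citric acid, mM | pH | pH rise from +50% flow | Bicarbonate left, mM |
|---|---|---|---|---|---|
| 100% | 0.05-0.20 | 694-174 | 1.7-2.5 | 0.10-0.20 | below 0.01 |
| 100% | 0.5-1.0 | 69-35 | 2.3-3.7 | 0.14-0.71 | at most 0.13 |
| 10% | 0.05-0.20 | 69-17 | 2.3-4.9 | 0.14-0.71 | at most about 2 |
| 10% | 0.5-1.0 | 7-3 | 3.5 to about 6.5 | about 0.15-0.70 | up to about 21 |

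The top of the last row is 6.3 or 6.5, depending on how dissolved CO₂ in the native saliva is counted.

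**Step 4: signal against artefact.** At 347 mM, a fivefold difference in native bicarbonate (5 against 25 mM) moves pH only from 1.88 to 2.14, a shift of 0.26. A 50% rise in flow at the same starting concentration moves it by 0.11-0.17, and 0.11/0.26 is already over 40% of that shift.

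**Step 5: bicarbonate.** Measured directly, it is consumed, as in the last column. If ionic balance means a charge gap over the listed ions, unmeasured citrate falls into the gap. With an assumed 15 mM bicarbonate and 5 mM phosphate, the gap reads about 17.8 mM at 7 mM citric acid and 20.8 mM at 347 mM. It is then too high, and it falls as flow rises. The two readings err in opposite directions.

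**Step 6: flow by weight.** Even if all 20 mg left the roll and was lost, weighed flow would change by 0.020/3 = 0.007 ml/min, the same offset in both arms.

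**The case against.** The best defence is that the damage is narrow and its size rests on assumptions. Acid recovery and collected volume are not in the documents. At 10% recovery and high flow the modelled pH approaches 6.5, where the acid no longer dominates. Both arms use the same rolls, so with equal flow the acid creates no difference between arms. At full recovery and 0.05-0.20 ml/min, the flow artefact is only 0.10-0.20 pH units. Composition is one part of one secondary outcome, and no success claim rests on it. All of this stands and limits the point.

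That the acid rolls are included is the natural reading of an unqualified sentence, not an explicit statement. Following the plan as written would still produce these measurements.

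A reader might infer more than the documents support:
- **That calcium and the other electrolytes are invalid.** Citric acid adds none of them. Binding alters ionised calcium, but the assay is not stated.
- **That ASC would falsely raise bicarbonate.** The direction depends on a cited method that cannot be checked here (step 5).
- **That all stimulated saliva is affected.** Stimulated whole saliva is obtained with paraffin wax and contains no citric acid.
- **That the plan contradicts its own call for uncontaminated saliva.** That remark sets gland saliva against the bacteria, epithelial cells and crevicular fluid in whole saliva. It does not concern the stimulus.

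**Conclusion.** The concern holds for pH, and in weaker form for bicarbonate, in one of the four saliva collections at each visit. Over an assumed 0.15-0.60 ml collected, 10-100% acid recovery and 5-30 mM native bicarbonate, sample pH is about 1.7-4.9 and largely reflects the stimulus. Milder values need low recovery together with high flow. A 50% rise in flow alone would raise pH by about 0.1-0.7 with unchanged secretion. A false difference between arms therefore requires a flow effect first, but a flow effect is what the trial hopes to see. Bicarbonate from these rolls is unreliable, with the direction of error unknown. Calcium is at risk only if the assay is ionised or otherwise citrate-sensitive.

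Neutral-roll saliva, paraffin-stimulated whole saliva, flow by weight, the primary safety outcome and the calculation of 15 per arm are not affected. The point should be corrected because the plan as written would yield a misleading secondary result, but it does not threaten the trial's main conclusions.

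**What to change.** In Assessment of salivary flow rate and objective treatment outcome, and in Chemical analysis of saliva, state that:

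- pH, bicarbonate and any citrate-sensitive assay, including ionised calcium if used, are analysed and interpreted only on neutral-roll submandibular saliva;
- the citric-acid rolls serve for flow by weight and for analytes that citric acid does not affect;
- calcium is measured as total or as ionised, whichever applies.

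The neutral-roll sample is already collected at every visit, so this needs no new sample and fewer assays. The cost is that no gland-specific stimulated pH or bicarbonate will be available. If stimulated values are wanted, paraffin-stimulated whole saliva is free of the acid. It must be labelled as whole saliva, because the plan itself calls whole saliva normally unsuitable for sensitive chemistry.

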Injection of the ASCs or placebo-suspensions into submandibular glands will be performed by the principal investigator ([name]) under local anesthesia using ultrasonic guidance and sterile technique. The ASCs will be suspended in isotonic NaCl (0.9 mg/ml) and human albumin (HA) 1% to a final volume of 2 ml. Placebo will be 2 ml of isotonic NaCl (0.9 mg/ml) and HA 1%. After receiving the ASC-suspension or placebo-suspension, the surgeon (the principal investigator) will identify the submandibular glands and inject the ASC suspension. Calculation of injected number of ASCs pr. participant rests on the following calculation: $Suspension_{ml} = 2.8 \times 10^6 \frac{ASC}{cm^3} \times volume_{cm^3}$, where volume is the volume of the submandibular gland, and a gland-volume of approx. $7\text{-}8 \text{ cm}^3$ is the norm. Therefore, the amount of ASCs given to each participant will be approx. $2.8 \times 10^6 \frac{ASC}{cm^3} \times 8cm^3 \times 2 = 4.48 \times 10^6 \text{ ASCs}$ in total. If the expanded number of ASCs does not fulfil the above criteria, it is accepted to diminish the number to a minimum of 50% of the calculated dose.

Justification for patient population

In order to standardize the participant population, we choose to only include participants treated for a human papilloma virus (HPV)-positive oropharyngeal squamous cell carcinoma, and exclude patients with severe salivary gland hypofunction and already manifest or near-manifest xerostomia, as this population most likely will not benefit from this treatment. This will be assessed by a preliminary questionnaire and a subsequent saliva flow rate measurement before inclusion.

Eligibility criteria

Evaluation of eligibility criterias and consent forms are collected by the Primary Investigator.

Inclusion criteria:

- Previous radiotherapy for a T1-T2 and N0, N1 or N2a, HPV-positive oropharyngeal squamous cell carcinoma with bilateral irradiation of the neck
- 2 years follow-up without recurrence
- Clinically reduced salivation and hyposalivation, evaluated by a screening
 - Unstimulated whole saliva flow rate in the range of 0.05-0.20 ml/min
- Informed consent
- Grade 1-3 xerostomia as evaluated by the “Udvalg for Kliniske Undersøgelser” (UKU) side effect rating scale[26].

Exclusion criteria:

- Any cancer in the previous 2 years
- Ongoing xerogenic medications
- Any other diseases of the salivary glands, e.g. Sjögrens syndrome, sialolithiasis, etc.

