We have strived to standardize saliva testing by performing tests at the same time of the day, and instructed and supervised by the same person ([name]). All participants are fasting two hours before the testing. This period is deemed useful to exclude any stimulants (e.g. lunch and drinking liquid) before testing, but might especially for participants with hyposalivation (e.g. participants with unstimulated whole saliva flow rate ≤ 0.10 ml/min) induce almost no secretion. Further, we perform in total four saliva measurements per visit (two tests for whole saliva (unstimulated/stimulated), and two tests for the submandibular glands (unstimulated/stimulated)) totaling to an effective period of 26 minutes of saliva testing. This is possibly too extensive for some participants meaning that the glands will when testing the submandibular glands not be capable of further secretion. Testing of the submandibular glands is performed following the stimulated testing of all glands (whole saliva). It might be an advantage to test the submandibular glands in a post-stimulated state, but it should be noted that the glands are stimulated. Testing of the submandibular glands is performed by placement of cotton rolls at the orifices under the tongue, and consequently the rolls will also collect saliva from the sublingual glands.

We have adjusted numbers of cell according to gland size based on experience from preclinical studies, but whether this is transferable to humans, and the dose is adequate remains unknown.

Following the liposuction 12-14 days prior to treatment, a core-needle biopsy of one of the submandibular glands (participants are randomized for biopsy of either the right or left gland) is performed. It cannot be excluded out that this procedure might inflict salivation and influence the effect of the ASCs. It is well-documented that ASCs secrete bioactive molecules that provide a regenerative microenvironment for a variety of injured tissues to limit damage and facilitate a regenerative response[35]. In this context, it is unknown whether injection to the submandibular glands regenerates only damaged tissue from the biopsy or also generates new or improved tissue.

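### Submandibular flow is analysed as percentage change from baseline, with no rule for a zero or near-zero baseline

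*Combined protocol and SAP*

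**What the plan says.** Combined protocol and SAP, Statistical analyses: "The results on salivary flow rate will be calculated as a percentage change in salivary flow rate (from baseline", with the change in the ASC arm compared with that in the control arm. No flow measure is excepted. A t-test for independent groups, with a non-parametric alternative, is named directly after the sentence on histology.

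Secondary outcomes lists "Unstimulated and stimulated whole saliva and selective submandibular saliva flow rate and composition of saliva". The section on assessment of salivary flow rate gives the purpose: "To assess ASC efficacy on the submandibular glands, saliva is also collected directly from the floor of the mouth", both unstimulated and stimulated. Flow is the weight gain of cotton rolls: "For both measurements, collections takes place during a period of 3 min".

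The only flow criterion in the inclusion criteria is "Unstimulated whole saliva flow rate in the range of 0.05-0.20 ml/min". There is none for submandibular flow.

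The Discussion makes two cautions. The two-hour fast might "induce almost no secretion", especially in participants with whole-saliva flow at or below 0.10 ml/min. The full set of four tests may also be too much for some participants, "meaning that the glands will when testing the submandibular glands not be capable of further secretion".

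No section gives a zero-baseline rule, a detection limit, an additive constant, a log scale or an analysis of flow in ml/min.

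**The concern.** Percentage change divides by the baseline. That is tolerable where the baseline is kept away from zero, as the entry criterion partly does for unstimulated whole saliva. It is fragile where nothing keeps the baseline away from zero. Submandibular flow is in that position: it has no entry limit, it is measured last, each collection is short, and the protocol itself raises the possibility of little or no secretion.

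Two things are at stake. A participant whose recorded baseline is zero has no value on the stated scale, and the plan does not say whether that person is left out or given a value. Leaving them out would remove the driest participants from the outcome closest to the injected glands. A participant with a baseline just above zero can get a very large percentage that dominates the arm's mean and SD.

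**Working it through.** **Inputs from the document.** Target difference 50%, SD of change 41%, two-sided alpha 0.05, power 90%, 15 per arm (Statistical analyses; Sample size calculation). Collection times are 15 min for unstimulated whole saliva, 5 min for stimulated whole saliva, and 3 min for each of the two submandibular tests, with 1 g taken as 1 ml. The document gives no submandibular flow values, so all such values below are assumptions.

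**1. The plan's own figure.** SD of change = 58/√2 = 41.0. n per arm = 2 × [41 × (1.960 + 1.282)/50]² = 14.13, rounded up to 15. Power at 15 is 0.916 by the normal approximation and 0.897 by the exact t-test. The stated 15 per arm reproduces. Its SD comes from unstimulated whole saliva.

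**2. Order and amount collected.** 15 + 5 + 3 + 3 = 26 minutes, with the submandibular tests last. At the entry floor, whole saliva yields 0.05 × 15 = 0.75 g. A submandibular flow of 0.005 ml/min yields 0.005 × 3 = 0.015 g.

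**3. The same gain on the percentage scale.** For a gain of 0.02 ml/min, 100 × 0.02/baseline gives:
- baseline 0.20: +10%
- baseline 0.05: +40%
- baseline 0.01: +200%
- baseline 0.002: +1000%
- baseline 0.00: undefined

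**4. One near-zero participant in an arm of 15.** (0.05 − 0.005)/0.005 = +900%, and 900/15 = 60 points on the mean, against a target of 50. Let the other 14 ASC participants and the control arm have SD 41, with control mean 0.
- No outlier, true difference 50: t = 50/[41 × √(2/15)] = 3.34, p = 0.002.
- Other 14 ASC participants average 50: mean = (14 × 50 + 900)/15 = 106.7, SD = 223, t = 106.7/√[(223² + 41²)/15] = 1.82, p = 0.08.
- Other 14 average 0: mean = 60, SD = 236, t = 60/√[(236² + 41²)/15] = 0.97.

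The outlier raises the mean but raises the SD more. A real effect is hidden, and where there is none the test does not become significant.

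**5. Undefined values.** If a share p of baselines reads zero, the chance of at least one among 30 is 1 − (1 − p)³⁰: 45% at p = 2%, 79% at 5%, 96% at 10%.

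**6. Simulation, 3,000 trials per setting.** Assumptions: 15 per arm, lognormal baseline with CV 58%, a true 50% gain with ASC, measurement error SD 0.01 to 0.02 ml/min, and readings rounded to 0.001. Participants with a zero baseline were dropped from both percentage analyses and kept in the ml/min analysis. True flow had no other visit-to-visit variation, so the methods can be compared but the power levels are not forecasts. Each range runs from the smaller to the larger error.

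| Mean baseline (ml/min) | Trials with an undefined value | t-test on % change, power | Rank test on % change, power | Follow-up ml/min with baseline covariate, power |
|---|---|---|---|---|
| 0.12 | 1–9% | 0.98–0.76 | 1.00–0.94 | 1.00–0.995 |
| 0.05 | 17–76% | 0.61–0.18 | 0.87–0.38 | 0.96–0.59 |
| 0.02 | 91–100% | 0.15–0.06 | 0.28–0.12 | 0.46–0.19 |

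**The case against.** **The warnings are hedged.** A reader might infer that the protocol expects almost no submandibular secretion. It does not say so. The remark on fasting says only that this might happen, concerns saliva testing in general, and takes its example group from whole-saliva flow. Only the later remark is about the submandibular test, and it is limited to some participants, as a possibility. Other text points the other way: the Discussion says that testing after stimulation might be an advantage and that the rolls also collect sublingual saliva, and the last test uses citric acid. All this makes an exact zero less likely, especially in the stimulated test, but does not exclude it.

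**There is a non-parametric fallback.** Whoever reads the t-test as covering flow must read the fallback as covering it too. A rank test limits the pull of an extreme value, and the simulation shows the benefit. It still cannot rank a value that does not exist.

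**The percentage might be meant for group means.** One zero would then do no harm. The text does not settle this, but a t-test with an SD of change scores implies a value per participant.

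**The scope is narrow.** Safety is the primary outcome. Unstimulated whole saliva is described as probably the most important flow parameter, and it has the entry floor. This stands: the point concerns two secondary measures.

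**The remedy is partly a choice.** A detection-limit rule or a log scale with a stated constant would also close the gap. That is fair. Analysis in ml/min is preferred because it needs no arbitrary constant and keeps every participant.

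**Conclusion.** The point holds as a gap in the analysis rule for unstimulated and stimulated submandibular flow. On the stated scale the result is undefined if a recorded baseline is zero and unstable if it is near zero, and the plan provides for neither. The size depends on flows that the documents do not give. At an assumed mean baseline of 0.12 ml/min few trials would meet an undefined value; at 0.05 or below it becomes common, and the percentage analysis loses much of its power.

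Three stronger conclusions that a reader might draw are not supported:
- That the formula certainly fails for some participants. It fails only at a recorded zero, and how often that occurs is unknown.
- That one dry participant would produce a false positive. In the worked cases the outlier inflates the SD and hides an effect.
- That the sample size is wrong for this reason. It reproduces, and it rests on unstimulated whole saliva.

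The change is worth making because these are the measures collected to show efficacy in the injected glands. It does not threaten the trial's primary objective.

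**What to change.** In Statistical analyses, give unstimulated and stimulated submandibular flow their own rule:
- analyse both in ml/min, comparing follow-up flow between arms with baseline flow in ml/min as covariate;
- keep zeros as observed values;
- report the number of participants with zero flow per arm and visit;
- if percentage change is kept, use it as a descriptive summary only, for participants with a baseline above zero, and give their number.

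The cost is a change of wording, best made before the allocation is revealed. Flow is already calculated in ml/min at every visit, so no new data or visits are needed. The downside is that the submandibular results no longer sit on the 50% scale of the sample size section and cannot be compared directly with that target.
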